## 5.0 STATISTICAL CONSIDERATIONS

### Sample Size Estimation

Based on data collected in the recently completed phase II study at MD Anderson which enrolled 65 women (60 evaluable) with locally advanced, approximately 32% will have PET imaging showing tumor metastasis to the pelvic nodes with negative paraaortic lymph nodes. Of these women, approximately 79% will truly have negative paraaortic lymph nodes. For them, 3 year overall survival with whole pelvis radiotherapy and concurrent chemotherapy is 75%. For the approximately 21% of women with false negative imaging (i.e. pathologically positive paraaortic lymph nodes with negative imaging), the 3 year overall survival with whole pelvis radiotherapy and concurrent chemotherapy is only 10%. If these metastases were known, however, and the radiation field was extended to cover the paraaortic basins, the 3 year overall survival improves to 50%. Thus, the expected overall survival without surgical staging would be approximately 61% and with preoperative paraaortic surgical evaluation would be 70%.

Assuming an accrual rate of 10 patients per month a sample size of 600 patients will yield 80% power with a 2-sided 0.05 significance level to detect a difference in 3-year overall survival of 61% and 70% between the patients without preoperative paraaortic surgical staging and the patients with preoperative paraaortic surgical staging. Accrual would take 5 years, and the study would be expected to take 7.6 years to complete, with a maximum 348 expected deaths. The accrual at LBJ will be 15 patients.

This sample size calculation includes an interim analysis for efficacy and futility once 174 deaths have been observed. The nominal p-value for the interim analysis of efficacy is 0.0031 and the nominal p-value for the interim analysis for futility is 0.3217. The nominal p-value for the final analysis is 0.049. The spending function approach of Lan and DeMets [16] with an O'Brien-Fleming [17] boundary for the interim analysis of efficacy and a Pocock [18] boundary for the interim analysis of futility were used in the sample size estimation. East 5.0 (Copyright © 2007, Cytel Inc., Cambridge, MA) was used to estimate the sample size and plan the interim analyses.

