### Analysis

We will use descriptive statistics to summarize patient demographic and clinical characteristics by treatment group.

We will estimate overall survival (OS) with the product limit estimator of Kaplan and Meier [19], and we will estimate the 3-year OS with a 95% confidence interval. We will also estimate the median OS with a 95% confidence interval. We will use the log-rank test to compare the 2 treatment groups with respect to OS.

We will also use the log-rank test for the interim analysis of OS, which will take place after 131 deaths have been observed. If the p-value from this test is  $< 0.0031$  the study will be stopped for efficacy, and if the p-value from this test is  $> 0.3217$  the study will be stopped for futility.

We will use Cox [20] proportional hazards regression to model OS as a function of treatment and other well-known and potential prognostic factors such as clinical stage, histology, and grade. We will estimate the hazard ratio for treatment (preoperative paraaortic surgical staging vs not) and other potential prognostic factors with 95% confidence intervals.

We will perform similar analyses for disease-free survival (DFS) as for OS.

We will tabulate the numbers of patients with particular short- and long-term morbidities including intraoperative and postoperative complications and treatment delay for each treatment group, and we will use the chi-square test to compare treatment groups with respect to the incidence of these morbidities.

For the treatment arm with pretreatment paraaortic surgical staging we will estimate the sensitivity of pretreatment radiologic staging examinations to detect metastatic disease with a 95% confidence interval. The findings of the pretreatment paraaortic surgical staging will be considered the true diagnosis of metastatic disease.

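### The interim is sized at 174 deaths but written to run at 131 with the same cut-offs, which lowers power from 80.4% to 74.6% at the planned effect

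*Combined protocol and SAP*

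**What the plan says.** Both statements are in section 5.0 of the combined protocol and SAP.

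- **Sample Size Estimation.** The claim is that "a sample size of 600 patients will yield 80% power with a 2-sided 0.05 significance level" to detect 61% against 70% at 3 years, with at most 348 deaths, 5 years of accrual at 10 patients a month, and an expected duration of 7.6 years. It adds: "This sample size calculation includes an interim analysis for efficacy and futility once 174 deaths have been observed". The efficacy cut-off is 0.0031, "the nominal p-value for the interim analysis for futility is 0.3217", and the final nominal level is 0.049. The boundaries are Lan-DeMets spending of O'Brien-Fleming type for efficacy and Pocock type for futility.
- **Analysis.** The interim is a log-rank test of overall survival, "which will take place after 131 deaths have been observed". It uses the same 0.0031 and 0.3217, and the study is to stop when either is crossed. Nothing makes the futility stop optional.

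One further rule bears on the death count. Section 4.0, Follow-Up/Surveillance, takes patients off study at death or 5 years after completing chemoradiation. Section 8.0 lists freedom from recurrence at 5 years as a reason for ending participation.

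**The concern.** The two parts of section 5.0 cannot both be followed, and nothing in the document says which count governs. This is more than a difference in timing. A futility cut-off is tied to the amount of information at the look. Taken to an earlier look, the same p-value stops more trials in which the treatment works as planned, because the expected test statistic is still small.

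If the Analysis part is followed as written, the trial does not have the power that justifies 600 patients and 348 deaths. A futility stop at 131 deaths, or a negative final result, would be read as coming from an 80%-powered trial when it did not.

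**Working it through.** **Inputs, all from section 5.0 (1:1 allocation also in 4.0).** 3-year survival 61% and 70%; interim at 174 or 131 deaths; final at 348; two-sided p-values 0.0031, 0.3217 and 0.049. The corresponding |Z| values are 2.958, 0.991 and 1.969.

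**Effect size.** The plan states no hazard ratio. Under proportional hazards, HR = ln(0.70)/ln(0.61) = 0.7216, and -ln(HR) = 0.3263.

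**Model.** The mean of Z after d deaths is 0.3263 × √(d/4). The correlation between looks is √(d1/348). Power = P(Z1 > 2.958) + P(0.991 < Z1 < 2.958 and Z2 > 1.969), with the futility stop obeyed.

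**Reproducing the plan's figure.** A fixed design needs (1.960 + 0.842)² × 4 / 0.3263² ≈ 295 deaths for 80%. With 348 deaths and no futility stop, power is about 86%. The 80% appears only once the stop at 174 is included:

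| | Interim at 174 | Interim at 131 |
|---|---|---|
| Mean of Z at interim | 2.152 | 1.867 |
| Mean of Z at 348 | 3.044 | 3.044 |
| Correlation | 0.707 | 0.614 |
| P(efficacy stop) | 0.210 | 0.138 |
| P(futility stop) | 0.122 | 0.188 |
| P(continue, then win) | 0.593 | 0.608 |
| **Power** | **80.4%** | **74.6%** |
| Power if futility is ignored | 86% | 86% |

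Simulated log-rank trials (8,000 for each count; 600 patients, uniform 5-year accrual) gave 80.6% and 74.6%.

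The stated duration also reproduces at 174. The interim falls at 5.08 years and the 348th death at 8.83 years. The chance of stopping at the interim is 0.210 + 0.122 = 0.332, so 0.332 × 5.08 + 0.668 × 8.83 = 7.6 years.

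**Which count the cut-offs fit.** The information fractions are 174/348 = 0.50 and 131/348 = 0.376.

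- Efficacy, 4 × [1 − Φ(2.2414/√t)]: 0.00305 at 0.50, matching 0.0031; 0.0005 at 0.376. The final levels are 0.0490 and 0.0498.
- Futility, β × ln(1 + (e − 1)t) with β of 0.196 to 0.20: the cut-off is p of about 0.32 at 174, matching 0.3217; about 0.54 at 131.

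With the interim at 131 and the recomputed cut-offs (0.0005, 0.54, 0.0498), power at HR 0.7216 is about 81%.

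**Can 348 deaths be reached?** Assume exponential survival at the planned rates, no loss to follow-up, and no deaths counted after a patient leaves the study.

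- Follow-up of 5.0 years from entry: 300 × (1 − 0.61^(5/3)) + 300 × (1 − 0.70^(5/3)) = 168.4 + 134.4 ≈ 303 deaths.
- Follow-up of 5.25 years (assuming about 3 months to the end of chemoradiation): 173.7 + 139.3 ≈ 313 deaths.

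With the interim at 174 and the final at 303 or 313, power is about 77% or 78%.

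**Sensitivity to rounding.** The plan's subgroup rates give 0.79 × 0.75 + 0.21 × 0.10 = 61.35% and 0.79 × 0.75 + 0.21 × 0.50 = 69.75%, so HR = 0.737. Under proportional hazards with looks at 174 and 348 deaths, power is 74.9%.

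**The case against.** The strongest reply is that sponsors often treat futility rules as guidance. If the rule is not acted on, power is about 86% at either count and the discrepancy costs nothing. The arithmetic is right, but it does not rescue the text. The Analysis part words the stop as mandatory, and the stated 80% is itself obtained only when the rule is followed. The sponsor may also say that 131 is a clerical remnant. That may be so, but the document does not say so, and 131 is the number in the instructions for the analysis.

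Three stronger readings are tempting and are not supported.

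- A reader might infer that the 80% is an arithmetic error. It is not; it reproduces for the effect and the interim that Sample Size Estimation names.
- A reader might infer from the subgroup rates that the trial was sized on the wrong effect and has only 75% power. The plan says "the expected overall survival without surgical staging would be approximately 61% and with preoperative paraaortic surgical evaluation would be 70", and 61.35% and 69.75% round to those figures. The shares are called approximate. Within the rounding of the inputs (occult-node share 20.5% to 22.5%, survival rates ±0.5 points), power at 174 runs from about 70% to 82%, a range that contains 80%.
- Because all the assumed benefit falls in the 21% with occult nodes, a reader might infer non-proportional hazards and far lower power. Hazards need not be proportional, but the documents give no subgroup curves. Two invented shapes gave about 38% and about 80%, so no figure can be attributed to the plan.

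The missing hazard ratio is a gap in detail, since it follows from 61% and 70% once proportional hazards are assumed.

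**Conclusion.** The contradiction is real and should be fixed. The interim rule in the Analysis part delivers 74.6% power at the planned effect, 5.8 points below the 80.4% of the design that was sized. It raises the chance of wrongly stopping for futility by 6.6 points (12.2% to 18.8%). These figures assume a constant hazard ratio of 0.722, a final analysis at 348 deaths, the p-values as printed, and a futility stop that is obeyed.

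The 80% in Sample Size Estimation stands for its own design. Whether 348 deaths are attainable is a separate condition on that figure. It depends on whether deaths are counted after patients come off study, which the plan does not make explicit.

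**What to change.** 1. Reconcile the interim count in section 5.0 by one of two routes:
   - change 131 to 174 in the Analysis part and leave the cut-offs as they are; or
   - keep 131, change 174 in Sample Size Estimation to match, and recompute the cut-offs in both parts (about 0.0005 for efficacy, 0.54 for futility and 0.0498 for the final test).
2. State the power for the count chosen: about 80% for the first route, about 81% for the second. Give the conditions with it: constant hazard ratio 0.722 and binding futility.
3. Before restating it, check the 348 deaths against the off-study rule in section 4.0 and the related entry in section 8.0. State whether deaths after that point are counted. If they are not, base the power on the deaths that can be observed.
4. Optionally, add a sensitivity line giving about 75% for the unrounded subgroup rates (HR 0.737, proportional hazards, looks at 174 and 348). It should not replace 61% and 70%.

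The cost of reconciling the count is wording in the two parts of section 5.0. With 10 patients a month and exponential survival, 174 puts the interim at about 5.1 years, just after accrual ends, instead of about 4.3. Recomputing for 131 avoids that delay.

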### Analysis

We will use descriptive statistics to summarize patient demographic and clinical characteristics by treatment group.

We will estimate overall survival (OS) with the product limit estimator of Kaplan and Meier [19], and we will estimate the 3-year OS with a 95% confidence interval. We will also estimate the median OS with a 95% confidence interval. We will use the log-rank test to compare the 2 treatment groups with respect to OS.

We will also use the log-rank test for the interim analysis of OS, which will take place after 131 deaths have been observed. If the p-value from this test is  $< 0.0031$  the study will be stopped for efficacy, and if the p-value from this test is  $> 0.3217$  the study will be stopped for futility.

We will use Cox [20] proportional hazards regression to model OS as a function of treatment and other well-known and potential prognostic factors such as clinical stage, histology, and grade. We will estimate the hazard ratio for treatment (preoperative paraaortic surgical staging vs not) and other potential prognostic factors with 95% confidence intervals.

We will perform similar analyses for disease-free survival (DFS) as for OS.

We will tabulate the numbers of patients with particular short- and long-term morbidities including intraoperative and postoperative complications and treatment delay for each treatment group, and we will use the chi-square test to compare treatment groups with respect to the incidence of these morbidities.

For the treatment arm with pretreatment paraaortic surgical staging we will estimate the sensitivity of pretreatment radiologic staging examinations to detect metastatic disease with a 95% confidence interval. The findings of the pretreatment paraaortic surgical staging will be considered the true diagnosis of metastatic disease.

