A recent review of three phase III chemoradiation studies by the Gynecologic Oncology Group also showed a survival advantage for women who underwent surgical staging when compared to those who were treated on radiologic findings alone [15]. On multivariate analysis, the relative risk of death for women staged radiologically was 1.46 when compared to women who had surgical staging ( $p=0.43$ ). For women with stage III/IV disease, surgical staging had an even bigger impact with surgically staged women having a 4 year overall survival of 54.3% compared to 40% for those who did not have surgical staging (RR 1.60,  $p=0.038$ ). Whether the survival benefit of surgical staging women with locally advanced cervical cancer is a result of tumor debulking, tailored radiotherapy, or a combination of the two is unknown. Regardless, these important findings should be explored prospectively.

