### **3.0 PATIENT ELIGIBILITY**

#### **3.1 Inclusion Criteria**

- 3.1.1 Women with clinical stage IB2-IVA cervical squamous cell carcinoma, adenosquamous, or adenocarcinoma
- 3.1.2 Women with FDG-PET positive or indeterminate pelvic lymph nodes or indeterminate low common iliac nodes (See addendum) and negative paraaortic nodes
- 3.1.3 Women with planned treatment of primary definitive chemoradiation therapy
- 3.1.4 4) An approved Informed consent and authorization permitting release of personal health information must be signed by the patient or guardian.

[figure not shown]

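### The log-rank tests that decide overall survival name no strata; stratifying them by clinical stage would be a cheap gain in efficiency and robustness, not the repair of an error

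*Combined protocol and SAP*

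**What the plan says.** Section 5.0 (Analysis) sets the final comparison: "We will use the log-rank test to compare the 2 treatment groups with respect to OS". For the interim look it says: "We will also use the log-rank test for the interim analysis of OS, which will take place after 131 deaths have been observed". The resulting p-value is compared with 0.0031 for efficacy and 0.3217 for futility. Neither sentence names strata or covariates.

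The same section plans a Cox regression "to model OS as a function of treatment and other well-known and potential prognostic factors such as clinical stage, histology, and grade", giving a treatment hazard ratio with a 95% confidence interval. No decision rule is attached to that model.

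Section 3.1 admits "Women with clinical stage IB2-IVA cervical squamous cell carcinoma, adenosquamous, or adenocarcinoma", so stage must be known before a woman can be randomized.

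Under Sample Size Estimation, "a sample size of 600 patients will yield 80% power with a 2-sided 0.05 significance level" for 3-year survival of 61% versus 70%. Both percentages describe the whole randomized population.

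**The concern.** Stages IB2 to IVA can be expected to differ in survival. When a prognostic factor is left out of a log-rank test, the treatment effect that the test sees is pulled toward the null. A stratified test compares women within the same stage group and avoids most of that loss. The plan already holds the data and already calls stage prognostic, but uses it only where nothing is decided.

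Two things are at stake. One is some average power. The other is the exposure of the single trial that will be run: if one arm happens to receive more advanced disease, the imbalance passes straight into the p-value that decides early stopping.

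**Working it through.** **1. Reproduce the plan's figure.** Inputs from Sample Size Estimation: 61% and 70% at 3 years, at most 348 deaths, an interim look at 174, nominal p-values 0.0031, 0.3217 and 0.049 (|Z| = 2.958, 0.991 and 1.969).

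- Under exponential survival, HR = ln(0.70)/ln(0.61) = 0.722, so |ln HR| = 0.326.
- The mean of Z after D deaths is |ln HR| × √D / 2, which is 2.152 at 174 and 3.044 at 348.
- Crossing efficacy at the interim: 1 − Φ(2.958 − 2.152) = 21.0%.
- Stopping for futility: Φ(0.991 − 2.152) = 12.3%.
- Adding the chance of continuing and then passing the final boundary (correlation √0.5) gives a total of **80.4%**.

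The stated 80% is therefore delivered by a test with no strata. The Analysis text puts the interim at 131 deaths. That conflict is a separate matter; 174 is used here because the boundaries fit it.

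**2. Average gain from stratifying.** Simulation: 600 women, 1:1, 5-year uniform accrual, looks at 174 and 348 deaths, the stated boundaries, and marginal 3-year survival held at 61% and 70%. The documents give neither stage mix nor stage hazard ratio. Assumed: 40% stage III/IVA, exponential survival, and one treatment hazard ratio within stage.

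| Assumed stage HR | Plain | Stratified | Gain (points) |
|---|---|---|---|
| 1.0 | 80.9% | 80.6% | −0.3 |
| 1.5 | 79.8% | 80.7% | 0.9 |
| 2.0 | 79.3% | 81.8% | 2.5 |
| 2.5 | 78.4% | 83.0% | 4.6 |

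Repeat simulations of the same mix gave gains of 0.7 and 1.2 at HR 1.5, 2.2 and 2.5 at HR 2, and 4.9 and 5.0 at HR 2.5. The small loss at HR 1.0 is simulation noise.

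**3. Which stage hazard ratio is plausible?** Only a rough orientation is possible. Section 2.0 cites 40% survival at 4 years for radiologically staged III/IV disease; under exponential survival this is 0.40^(3/4) = 50% at 3 years. Set against the 61% control assumption:

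- With a 30% share of III/IV: the rest survive at (0.61 − 0.30 × 0.503)/0.70 = 0.656, so HR = ln(0.503)/ln(0.656) = 1.6.
- With a 50% share: (0.61 − 0.50 × 0.503)/0.50 = 0.717, so HR = 2.1.

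This mixes two different populations. It only suggests that 1.5 to 2 is a sensible central range.

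**4. The plan's own mechanism.** The survival figures are built from 79% truly node-negative women and 21% with missed paraaortic disease:

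- Control: 0.79 × 75% + 0.21 × 10% = 61.35%.
- Surgical staging: 0.79 × 75% + 0.21 × 50% = 69.75%.

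All the benefit lies in a subgroup that stage does not identify. Simulating this mixture (exponential survival within class, stage HR 2, 40% III/IVA, stage independent of nodal status) gave a gain of 0.7 points (SE 0.3). Read this only as a difference between the two tests.

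**5. Chance imbalance.** Under simple randomization with 300 per arm, the SD of the between-arm difference in the III/IVA share is √(0.4 × 0.6 × 2/300) = 0.04, or 4 percentage points. At stage HR 2 (4,000 runs):

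- Surgical arm 4 points heavier in III/IVA: power 73.8% plain, 82.8% stratified.
- 8 points heavier: 62.3% plain, 81.0% stratified; futility stopping 21.8% plain, 12.2% stratified.

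An imbalance the other way would flatter surgery. These figures are conditional on the imbalance. The averages in step 2 already include such draws, so the two must not be added.

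**The case against.** The case against acting is substantial, and most of it stands.

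- **No shortfall.** A reader might infer that the trial is underpowered, or its primary test wrong, because stage is left out. The documents do not support this. The plain log-rank test is valid, 80% reproduces for it, and no power claim relies on strata.
- **Not without benefit.** A reader might say the plain test gives up power for nothing in return. In fact it needs no stage cut-points, avoids sparse strata such as IVA, and tests the whole-population contrast on which the trial was sized.
- **Size rests on assumptions.** Gains of up to 6 points can be obtained for the final test taken alone, but the plan has an interim look with futility stopping, so that is not this design.
- **Background text.** The statement "For women with stage III/IV disease, surgical staging had an even bigger impact" concerns the effect of surgical staging within advanced disease. It does not measure how prognostic stage is.
- **Randomization.** Section 6.0 as available lacks the name of the method. It cannot be inferred that allocation ignores stage. If allocation is balanced on stage, the exposure in step 5 shrinks, and the analysis should then carry the same factor.
- **Adjusted Cox model.** A stage-adjusted hazard ratio is already planned. This helps interpretation but not the decision, because the boundaries apply to the log-rank p-value and the covariate list is introduced only by way of example. If the two analyses disagreed, the plan gives no rule for which prevails.

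What survives is that the deciding test ignores a known baseline factor which could be used at almost no cost.

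**Conclusion.** The point holds as a recommended improvement in efficiency and robustness, with moderate confidence in its size. Absence of strata is the natural reading of the text, not a stated choice.

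The direction is secure: a stage-stratified test keeps the type I error and loses essentially nothing if stage has no effect. The average gain is modest, at about 1 to 3 points for a stage hazard ratio of 1.5 to 2, about 5 points at 2.5, and about 0 to 1 point under the plan's occult-node mechanism. The stage share, the stage hazard ratio and, outside that mechanism, the constant within-stage treatment effect are all assumed. Protection of the interim futility and efficacy calls against a chance stage imbalance is the more practical reason to change, subject to how randomization is actually done.

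**What to change.** In section 5.0 (Analysis), state that:

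- the interim and final OS comparisons are log-rank tests stratified by prespecified clinical stage groups, for example IB2-II versus III-IVA, and by any factor used in randomization;
- the treatment hazard ratio comes from the Cox model with the same strata;
- the unstratified log-rank test is a sensitivity analysis;
- the same approach applies to DFS.

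The cost is a short text change, with no extra patients or data. The stage cut-points must be fixed before any outcome data by arm are seen, and two groups keep the strata from becoming sparse. The test then addresses the within-stage effect, so the marginal 61% versus 70% contrast is shown by the Kaplan-Meier 3-year estimates that the plan already includes. The sample size and nominal boundaries need not change on this account.

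### The 80% power assumes a constant hazard ratio, but the subgroup rates behind 61% vs 70% imply an effect that wanes, and under them the planned log-rank test has less than 80% power

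*Combined protocol and SAP*

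**What the plan says.** Section 5.0, Sample Size Estimation, builds the target difference from two groups of women.

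- Node-negative: "Of these women, approximately 79% will truly have negative paraaortic lymph nodes", and "For them, 3 year overall survival with whole pelvis radiotherapy and concurrent chemotherapy is 75"%. No difference between arms is assumed for them.
- Occult paraaortic disease (21%): untreated above the pelvis, "the 3 year overall survival with whole pelvis radiotherapy and concurrent chemotherapy is only 10"%; if the disease is found and the field extended, "the 3 year overall survival improves to 50"%.

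The trial is then sized at 600 patients for 80% power, two-sided 0.05, "to detect a difference in 3-year overall survival of 61% and 70"%. There is a maximum of 348 deaths and one interim look at 174. The nominal p-values are 0.0031 (efficacy) and 0.3217 (futility) at the interim and 0.049 at the end.

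Section 5.0, Analysis, names the test: "We will use the log-rank test to compare the 2 treatment groups with respect to OS". The interim uses the same test. No weighting, no allowance for non-proportional hazards and no survival shape within the subgroups is stated. The Follow-Up/Surveillance text in Section 4.0 ends study follow-up five years after chemoradiation.

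**The concern.** The model that justifies the effect and the model that yields the power are different. In the first, the control arm loses its high-risk women early. The women rescued in the surgical arm remain at higher risk than node-negative women and die later, when few high-risk women are left among the controls. The arm-level hazard ratio therefore starts well below 1 and rises. The second model holds the ratio fixed throughout.

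An unweighted log-rank gives late deaths the same weight as early ones, so deaths that occur once the ratio is near or above 1 add noise or cancel the early difference. If staging does what the protocol assumes, the chance of showing it is lower than readers of the sample size section are told.

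**Working it through.** **Inputs (Section 5.0):** 79%/21% split; 3-year OS 75%, 10% and 50%; 600 patients, 1:1, 10 per month for 5 years; looks at 174 and 348 deaths; nominal p-values 0.0031, 0.3217 and 0.049, i.e. Z of 2.96, 0.99 and 1.97.

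**1. Reproduce the plan.** Proportional hazards at 61% vs 70% give HR = ln(0.70)/ln(0.61) = 0.722. Expected Z = √(D/4) × |ln HR|: √(174/4) × 0.326 = 2.15 at the interim and √(348/4) × 0.326 = 3.04 at the end. Integrating over the two looks gives power of 80.4%. The time to 348 deaths is 8.8 years. The printed 7.6 years is the expected duration allowing for early stopping: 0.33 × 5.07 + 0.67 × 8.83 = 7.59. The plan's figures are internally correct under this model.

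**2. Rounding.** The mixture gives 0.79 × 75 + 0.21 × 10 = 61.35% and 0.79 × 75 + 0.21 × 50 = 69.75%. Then HR = ln(0.6975)/ln(0.6135) = 0.737, and power is 74.9%. About 5 points go here.

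**3. Arm-level hazard ratio under the subgroup rates.** The documents give only 3-year rates. Assume constant hazards within subgroups: −ln(0.75)/3 = 0.096, −ln(0.10)/3 = 0.768 and −ln(0.50)/3 = 0.231 per year. At time 0 the ratio is (0.79 × 0.096 + 0.21 × 0.231)/(0.79 × 0.096 + 0.21 × 0.768) = 0.52. Later values, with each subgroup weighted by its survivors:

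| Year | 1 | 2 | 3 | 4 | 5 |
|---|---|---|---|---|---|
| HR | 0.69 | 0.85 | 0.98 | 1.06 | 1.10 |

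It passes 1 at about 3.2 years.

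**4. What a constant ratio would require.** Keep the constant hazards for node-negative women and for control women with occult disease, and hold the arm-level ratio at 0.737. Survival of the rescued women must then be (S_C^0.737 − 0.79 × S_neg)/0.21, where S_C is control-arm survival and S_neg node-negative survival.

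- Year 3: (0.6975 − 0.5925)/0.21 = 50%.
- Year 5: S_neg = 0.619, S_C = 0.494; (0.594 − 0.489)/0.21 = 50%.
- Year 7: S_neg = 0.511, S_C = 0.405; (0.513 − 0.404)/0.21 = 52%.

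Survival cannot rise, so on these hazards the ratio cannot stay constant.

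**5. Log-rank power under the subgroup rates.** Simulation of the stated two-look rule with uniform accrual over 5 years:

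| Survival shape through the same 3-year rates | Data cut | Power | Mean Z, interim → final |
|---|---|---|---|
| Constant hazards within subgroups | 348 deaths (about 9.7 years) | about 38% | 2.15 → 1.54 |
| Weibull and lower-late-hazard variants | 348 deaths | 26% to 49% | falls in all |
| Constant hazards within subgroups | about 5.2 years per patient (about 292 deaths) | about 47% | 2.16 → 1.86 |
| Constant hazards within subgroups | 7.6 years (about 284 deaths) | about 47% | 2.14 → 1.86 |
| Hazards quartered after year 3 | about 5.2 years per patient | about 60% | 2.29 → 2.22 |
| Plateau after year 3 | about 5.2 years per patient | about 65% | 2.36 → 2.36 |

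The 5.2 years stands for the Section 4.0 limit plus an assumed treatment period. The same simulation approach returns 80% under constant 61%/70% hazards. The Analysis text puts the interim at 131 deaths rather than 174. That is a separate inconsistency and leaves the first row at 38.0%.

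**The case against.** The plan's 80% is stated for 61% vs 70%, and for those inputs it is right. The log-rank is prespecified and remains a valid test without proportional hazards, and 3-year OS with confidence intervals is also planned. All of that stands: this is not an arithmetic error.

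The 38% is one scenario. The documents fix survival at 3 years and nothing else, and the follow-up limit in Section 4.0 makes 348 deaths hard to reach (roughly 285 to 292 under constant subgroup hazards). The 47% or the 60% to 65% figures may be nearer what would happen. This also stands, so a range is needed. It does not rescue the 80%: every shape tested falls short.

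A reader might infer that the trial is more likely than not to miss a real benefit, or that deaths after the interim always weaken the result. Neither follows from the documents. Power exceeds 50% in the sharp-drop and plateau cases, and with a plateau the mean Z does not fall.

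A reader might also conclude that the primary test should become an early-weighted log-rank. That is debatable. Fleming-Harrington (rho = 1, gamma = 0) gives about 53% at 348 deaths and up to 69% in the more favourable shapes, still short of 80%. With constant subgroup hazards its mean Z also falls (2.32 to 2.02). At 174 deaths its information fraction is about 0.65 rather than 0.5, so the interim boundary would have to be re-derived. Down-weighting late deaths is also a contestable answer to an objective framed as longer overall survival. A plain comparison of 3-year proportions with 300 per arm reaches only 58% to 64%.

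**Conclusion.** The concern holds as a mismatch between the effect model and the power model. The 80% applies to a log-rank under a constant hazard ratio of about 0.72. Under the plan's own subgroup rates, the log-rank has less than 80% power in every survival shape tested, from 26% to about 65%, with about 38% for constant subgroup hazards run to 348 deaths. Rounding explains about 5 points; the rest comes from the non-proportional effect and the data cut. The direction is firm. The size rests on a survival shape and an effective follow-up that the documents leave open, so no single figure should be presented as the trial's true power.

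**What to change.** In Sample Size Estimation, state that 80% assumes proportional hazards at 61% vs 70%. Add the log-rank power under the listed subgroup rates as a range, with the survival shape and data cut behind each figure, including the Section 4.0 follow-up limit.

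In Analysis, keep the log-rank as the primary test. Pre-specify a Fleming-Harrington (rho = 1, gamma = 0) log-rank as a sensitivity analysis, reported next to the 3-year OS estimates already planned.

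The cost is a less favourable stated power and one extra analysis. Sample size, primary test and interim boundaries are unchanged. The sensitivity analysis does not restore 80% power; it shows whether an early benefit has been diluted by later deaths.
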